#### (4) Prevention and management of expected ADRs:

The actual ADR treatment measures will be taken by the investigator according to the actual situation of the subjects in combination with clinical practice and relevant guidelines. The following suggestions are only for reference. For common ADRs in the dose escalation trial, prophylaxis can be given in advance during the expansion trial.

- Diarrhea: Among the adverse effects of FGFR inhibitor, diarrhea's incidence is 15%-60%, which may be related to preventing the binding of FGF19 and FGFR4. The homeostasis of bile acids will be regulated after FGF19 binding with FGFR4, while bile acids have effects on colonic mucosal permeability. It is recommended to continue the study treatment at the original dose level, and loperamide, probiotics, and smecta (montmorillonite powder) should be given to treat ADR at the same time when drug-related grade 1-2 diarrhea occurs during the clinical trial. If grade 3 diarrhea occurs, it is recommended to interrupt the study treatment, and loperamide, probiotics, and smecta (montmorillonite powder) should be given to treat ADR at the same time (codeine and prophylactic antibiotics may be used if necessary), the addition of somatostatin may be considered in severe conditions. If grade 4 diarrhea occurs, it is recommended to discontinue the study treatment permanently, at the same time, the above symptomatic treatment should be given.
- Asthenia: FGFR4 has the function of regulating the differentiation of muscle cells and tissue repair. If asthenia occurs in the trial, it is considered to be related to the inhibition of the physiological function of FGFR4. It is recommended to continue the study treatment at the original dose level, and have more rest at the same time when drug-related grade 1-2 asthenia occurs during the clinical trial. If grade 3 asthenia occurs, it is recommended to discontinue the study treatment permanently and have more rest at the same time.
- Nausea/vomiting: They are not caused by FGFR4 physiological mechanism and can be considered as the gastrointestinal irritation of the investigational drug. It is recommended to continue the study treatment at the original dose level, and metoclopramide and so on should be given to treat ADR at the same time when drug-related grade 1-2 nausea/vomiting occurs during the clinical trial. If grade 3 nausea/vomiting occurs, it is recommended to interrupt the study treatment, and metoclopramide and so on should be given to treat ADR at the same time. If grade 4 nausea/vomiting occurs, it is recommended to discontinue the study treatment permanently, and the above symptomatic treatment should be given at the same time.

Fever: Generally, it may be the non-inflammatory fever caused by the death or rupture of cancer cells. It is recommended to continue the study treatment at the original dose level, at the same time, strengthen body temperature monitoring, and perform physical cooling, ice compress and drink warm water if necessary when drug-related grade 1 fever occurs during the clinical trial. If grade 2 fever occurs, it is recommended to continue the study treatment at the original dose level, and cooling medications (e.g., dexamethasone, loratadine, etc.) should be given to treat ADR at the same time. If grade 3 fever occurs, it is recommended to interrupt the study treatment and the above symptomatic treatment should be given at the same time. If grade 4 fever occurs, it is recommended to discontinue the study treatment permanently, and the above symptomatic treatment should be given at the same time.

➤ Hepatotoxicity: It is considered to be caused by damage to liver cells or functional overload. It is recommended to continue the study treatment at the original dose level, and hepatoprotective medications [e.g., Chinese traditional patent polyene glutathione, phosphatidylcholine, reduced magnesium isoglycyrrhizinate, simetai (adenosylmethionine butanedisulfonate enteric-coated tablet)] should be given for symptomatic treatment at the same time when drug-related grade 1-2 hepatotoxicity occurs during the clinical trial. If grade 3 hepatotoxicity occurs, it is recommended to interrupt the study treatment and the above symptomatic treatment should be given at the same time. If grade 4 hepatotoxicity occurs, it is recommended to discontinue the study treatment permanently, and the above symptomatic treatment should be given at the same time.

Any prescription drugs, over-the-counter drugs, natural extracts, nutritional supplements, traditional Chinese medicines, herbal medicines and vitamins should be reviewed and approved by the investigator. All information on concomitant medications should be recorded in the subjects' medical records and reported on the eCRF.

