- Diarrhea: Among the adverse effects of FGFR inhibitor, diarrhea's incidence is 15%-60%, which may be related to preventing the binding of FGF19 and FGFR4. The homeostasis of bile acids will be regulated after FGF19 binding with FGFR4, while bile acids have effects on colonic mucosal permeability. It is recommended to continue the study treatment at the original dose level, and loperamide, probiotics, and smecta (montmorillonite powder) should be given to treat ADR at the same time when drug-related grade 1-2 diarrhea occurs during the clinical trial. If grade 3 diarrhea occurs, it is recommended to interrupt the study treatment, and loperamide, probiotics, and smecta (montmorillonite powder) should be given to treat ADR at the same time (codeine and prophylactic antibiotics may be used if necessary), the addition of somatostatin may be considered in severe conditions. If grade 4 diarrhea occurs, it is recommended to discontinue the study treatment permanently, at the same time, the above symptomatic treatment should be given.
- Asthenia: FGFR4 has the function of regulating the differentiation of muscle cells and tissue repair. If asthenia occurs in the trial, it is considered to be related to the inhibition of the physiological function of FGFR4. It is recommended to continue the study treatment at the original dose level, and have more rest at the same time when drug-related grade 1-2 asthenia occurs during the clinical trial. If grade 3 asthenia occurs, it is recommended to discontinue the study treatment permanently and have more rest at the same time.
- Nausea/vomiting: They are not caused by FGFR4 physiological mechanism and can be considered as the gastrointestinal irritation of the investigational drug. It is recommended to continue the study treatment at the original dose level, and metoclopramide and so on should be given to treat ADR at the same time when drug-related grade 1-2 nausea/vomiting occurs during the clinical trial. If grade 3 nausea/vomiting occurs, it is recommended to interrupt the study treatment, and metoclopramide and so on should be given to treat ADR at the same time. If grade 4 nausea/vomiting occurs, it is recommended to discontinue the study treatment permanently, and the above symptomatic treatment should be given at the same time.

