#### (2) Non-hematologic toxicity

- 1) Grade ≥4 non-hematologic toxicity. Note: Toxicities with no safety risk at the discretion of the investigator are excepted, such as grade 4 GGT increased and alkaline phosphatase (ALP) increased.
- 2) Grade 3 non-hematologic toxicity (including but not limited to hepatobiliary disorders). Note: Toxicities with no safety risk at the discretion of the investigator (such as grade 3 nausea, vomiting, diarrhea, asthenia, constipation, loss of appetite, mucositis, GGT increased, ALP increased) are not defined as DLT, but they will be defined as DLT when the toxicities do not recover to grade ≤2 within 7 days under the circumstance of symptomatic supportive treatment are permitted.

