## (3) Other conditions

1) The grade is elevated from baseline with clinically significant and/or unacceptable toxicity, which is judged as a DLT by the SMC.

- 2) Drug discontinuation lasting 7 days or more due to drug-related toxicity.
- 3) The dose received by the subject during the DLT observation period is less than 75% of the scheduled dose due to toxicities attributable to study drug, and the investigator believes that it should be considered as a DLT.

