Grade 4	Discontinue permanently.  Note: Continue the study treatment at the dose reduced by one level c at the discretion of the investigator if the grade 4 increase in blood bilirubin is only due to the increase in indirect bilirubin (unconjugated bilirubin), and hemolytic factors (e.g., peripheral blood smear examination and haptoglobin assay) have been excluded according to the guidelines of each study center.		
AST or ALT increased			
Grade 1-2	Continue the study treatment at the original dose level.		
Grade 3	
 
Administration interruption until the toxicity is resolved to grade ≤2 (liver cancer or liver metastases) or grade ≤1.
 
Resume the study treatment at the original dose level if the toxicity is resolved within ≤7 days.
 
Continue the study treatment at the dose reduced by one level c if the toxicity is resolved within 7-14 days.
 
Discontinue permanently if the toxicity is resolved within >14 days.
 
		
Grade 4	Discontinue permanently.		
Other nonhematologic toxicity			
Grade 1-2	Continue the study treatment at the original dose level.		
Grade 3 toxicities with no safety risk at the discretion of the investigator, such as grade 3 nausea, vomiting, diarrhea, asthenia, constipation, loss of appetite, mucositis, GGT increased and ALP increased.	Administration interruption until the toxicity is resolved to grade $\leq 2$ . Resume the study treatment at the original dose level after the toxicity is resolved to grade $\leq 2$ .		

Grade 3	
Note: Toxicities with no safety	Administration interruption until the toxicity is resolved to
risk at the discretion of the	grade ≤2 or grade ≤1.
investigator are excepted, such as	Resume the study treatment at the dose reduced by one
grade 3 nausea, vomiting,	level c after the toxicity is resolved to grade 2 (only when
diarrhea, asthenia, constipation,	the investigator believes resuming the study treatment
loss of appetite, mucositis, GGT	poses no safety risk to the subject) or grade ≤1.
increased and ALP increased.	
	Administration interruption until the toxicity is resolved to
	grade $\leq 2$ or grade $\leq 1$ .
Abnormal grade 4 laboratory test	Resume the study treatment at the dose reduced by one
results that are not life-threatening	level c after the toxicity is resolved to grade 2 (only when
judged by the investigator (such as	the investigator believes resuming the study treatment

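### Grade 3 asthenia: the management advice recommends a permanent stop while the dose-modification table interrupts and resumes, and in one narrow case the choice changes a DLT count

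*Protocol*

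**What the plan says.** **Management advice.** Section 6.2 (4) lists suggestions for expected adverse drug reactions. Its entry on asthenia says: "If grade 3 asthenia occurs, it is recommended to discontinue the study treatment permanently and have more rest at the same time". The Synopsis repeats this under Concomitant Medications: "If grade 3 asthenia occurs, it is recommended to discontinue the study treatment permanently". The list is introduced in Section 6.2 (4) with "The following suggestions are only for reference". For the other reactions listed (diarrhea, nausea/vomiting, fever, hepatotoxicity), grade 3 leads to interruption and only grade 4 to a permanent stop.

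**Dose-modification table.** The table in Section 6.1.2, also in the Synopsis, has two grade 3 rows for other non-hematologic toxicity. The first covers "Grade 3 toxicities with no safety risk at the discretion of the investigator, such as grade 3 nausea, vomiting, diarrhea, asthenia" and similar events. Dosing is interrupted, and then: "Resume the study treatment at the original dose level after the toxicity is resolved to grade" 2 or lower. The second row covers grade 3 toxicities outside that exception: interrupt, then resume one dose level lower. The heading above the table limits it to the time after the DLT window in escalation and to the dosing period in expansion. For the DLT window itself, Section 6.1.2 leaves interruption for non-DLT toxicities to the investigator's assessment.

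**DLT definition.** Section 4.1.1.4 (2) makes grade 3 non-hematologic toxicity a DLT. It exempts events that the investigator judges to carry no safety risk, "such as grade 3 nausea, vomiting, diarrhea, asthenia, constipation, loss of appetite, mucositis" among them, provided that they recover to grade 2 or lower within 7 days. Section 4.1.1.4 (3) separately lists as a DLT: "Drug discontinuation lasting 7 days or more due to drug-related toxicity". That item names no exempt toxicities.

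**The concern.** The two management texts cannot both be followed for grade 3 asthenia. With 3 to 6 sites planned (Section 4.8), the same event could end treatment at one site and lead to resumption at another, so discontinuation and exposure would depend partly on which page was read.

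The second issue is the count. DLT is a primary endpoint of the escalation trial (Section 7.1). It drives the 3+3 rule and the 1/6 thresholds for the MTD and for opening expansion. If following the asthenia advice can turn an exempt event into a DLT, a dose decision could rest on a management suggestion and not on the toxicity. In expansion, events meeting the DLT definition are counted as AESIs (Section 8.5), so the same ambiguity can carry over there.

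**Working it through.** **Step 1. The two management texts side by side, for grade 3 drug-related asthenia.**

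| Judgement by the investigator | Section 6.1.2 table | Section 6.2 (4) |
|---|---|---|
| No safety risk | Interrupt, resume at the same dose | Permanent stop |
| Safety risk | Interrupt, resume one level lower | Permanent stop |

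No reading of the table agrees with the advice. By the table's heading, this conflict lies after the DLT window in escalation and throughout expansion.

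**Step 2. Inside the DLT window.** The table does not apply. Section 6.1.2 leaves interruption for non-DLT toxicity to the investigator. Section 6.2 (4) speaks of events during the trial in general, so it is the only management advice specific to asthenia there.

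**Step 3. DLT status inside the window.**

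- Judged a safety risk: DLT under 4.1.1.4 (2), whatever is done with the drug.
- Judged no safety risk, not recovered to grade 2 or lower within 7 days: DLT under 4.1.1.4 (2), whatever is done.
- Judged no safety risk, recovered within 7 days, dosing resumed within 7 days: not a DLT.
- Judged no safety risk, recovered within 7 days, drug permanently stopped early enough: DLT under 4.1.1.4 (3), second item.

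Only the last two differ by management choice. In the last case the subject stays in the DLT set and is not replaced. Sections 4.1.1.5 and 10.2 remove only subjects under-dosed for reasons other than drug toxicity.

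**Step 4. How early is early enough.** The window holds 1 single dose + 21 daily doses = 22 doses, and 75% of 22 is 16.5. If the first omitted dose is on C1Dk, doses taken = 1 + (k − 1) = k, and days off drug inside the window = 21 − k + 1.

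| First omitted dose | Doses taken | Share of 22 | Days off in window |
|---|---|---|---|
| C1D15 | 15 | 68% | 7 |
| C1D16 | 16 | 73% | 6 |
| C1D17 | 17 | 77% | 5 |

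A stop at C1D15 or earlier gives 7 or more days off drug inside the window. Up to C1D16 it also meets the dose part (below 75%) of the third item in 4.1.1.4 (3), but that item additionally needs the investigator to consider the event a DLT.

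**Step 5. Effect on the 3+3 rule (Section 4.1.1.3).** One such event turns 0/3 (escalate) into 1/3 (three more subjects), or 1/6 (escalate) into 2/6 (escalation stops).

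**Step 6. Illustration with assumed rates.** The protocol gives no rate for this event. Let p be the risk of any other DLT and a the risk of the narrow event in Step 3 with an early permanent stop, taken as independent. The total DLT risk is P = 1 − (1 − p)(1 − a), and the chance of escalating past a dose is (1 − P)³ + 3P(1 − P)²(1 − P)³. With p = 10%, this is 0.906 at a = 0. It is 0.875, 0.824 and 0.730 at a = 2%, 5% and 10%. For p from 5% to 20%, the fall over these values of a is about 2 to 18 percentage points. These figures show sensitivity only and do not estimate what will happen.

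**The case against.** The strongest reply is that the protocol ranks the texts. Section 6.1.2 says that actions will follow its table, while Section 6.2 (4) leaves the actual measures to the investigator and labels its list as reference only. This favours the table, but no sentence gives it precedence, and the advice remains a specific recommendation that contradicts it.

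A reader might infer that the table and the advice conflict inside the DLT window. They do not: the table does not cover that period, and the rule that does leaves the decision to the investigator. A reader might also infer that the choice of page decides the DLT status of grade 3 asthenia generally. It does not: the exemption covers only events judged to carry no safety risk, and asthenia judged a risk or not recovered in 7 days is a DLT in any case.

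The 12.5% asthenia figure in Section 1.3 should not be read as the frequency of this problem. It is treatment-related asthenia of any grade in the once-daily group of another drug.

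Two further points stand in part. The 7-day discontinuation item makes DLT status depend on the stop decision for any drug-related toxicity. Asthenia differs in that a listed exempt toxicity is also one for which a permanent stop is advised at grade 3. And the SMC (Section 4.1.1.6) may meet before each escalation and could notice divergent handling, but it is given no rule for this case.

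**Conclusion.** The inconsistency is real and stands on the text alone: a permanent stop is recommended in one place and interruption with resumption is specified in another, with no stated precedence. Its direct reach is the post-DLT period in escalation and all of expansion.

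The DLT consequence is narrow. It needs an event inside the window that is drug-related, judged to carry no safety risk, recovered within 7 days, and followed by a permanent stop by about C1D15. The date assumes that the 7 days off drug must fall within the window, which the protocol does not spell out, and that a permanent stop counts as a discontinuation of 7 days or more, its plain meaning. In that case one event shifts a group from 0/3 to 1/3 or from 1/6 to 2/6. How often this would happen cannot be computed from the protocol. The point merits correction before sites rely on either text, but it does not undermine the escalation design.

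**What to change.** Reconcile the asthenia entry in Section 6.2 (4) and its copy in the Synopsis with the grade 3 rows of the table in Section 6.1.2 and its Synopsis copy, so that grade 3 asthenia has one consistent action. In Section 4.1.1.4, state how a permanent stop for an otherwise exempt grade 3 toxicity is counted when the exemption in (2) and the 7-day item in (3) point in different directions, and whether the 7 days must lie inside the window. Grade 3 asthenia would then have one DLT status. Which action is right is for the clinical team.

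The cost is a text change to the protocol and Synopsis. It needs no extra visits, samples or subjects.

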#### 6.3 Compliance of Subjects

The investigator should emphasize the importance of compliance to the subjects during the process of informed consent. During the process of the trial, if a subject's compliance is poor, the investigator should find the cause and actively take corresponding measures (e.g., emphasizing the importance of protocol compliance to the subject), and completely record the related non-compliance, cause and measures taken.

The investigator should timely and accurately collect and record the planned dose, actual dose, and date of administration of each subject. In principle, the actual dose should be consistent with the planned dose.

The investigator should judge the study treatment compliance according to the medication details.

Compliance = actual dose/planned dose  $\times$  100%.

Subjects taking medication within the range of 80%-120% will be considered to have good treatment compliance.

# 7. Study Endpoints

#### 7.1 Dose Escalation Trial

#### **Primary endpoints:**

- Safety and tolerability of BB102 tablets (fasted or fed): Incidences of AEs and SAEs; abnormalities or changes in laboratory tests, vital signs, ECG, physical examination and ECOG score.
- DLT of BB102 tablets (fasted or fed): Classification, severity and frequency of DLT.

# **Secondary endpoints:**

- PK parameters of BB102 tablets (fasted): Maximum plasma concentration (Cmax), time to maximum plasma concentration (Tmax), lag time (tlag), elimination rate constant (Kel), T1/2, area under the concentration-time curve from 0 to the time point of last quantifiable concentration (AUC0-t), area under the concentration-time curve from time 0 to infinity (AUC0-inf), apparent clearance (CLz/F), apparent volume of distribution (Vz/F), mean residence time (MRT), steady-state minimum plasma concentration (Css, min), steady-state maximum plasma concentration (Css, max), average steady-state plasma concentration (Css, av), area under the concentration-time curve during a dosing interval at steady state (AUCss), steady-state degree of fluctuation (DF) and accumulation ratio (Rac) of BB102 (and its main metabolites, if applicable).
- PK parameters of BB102 tablets (fed):  $C_{max}$ ,  $T_{max}$ ,  $t_{lag}$ , Kel,  $T_{1/2}$ ,  $AUC_{0-t}$ ,  $AUC_{0-inf}$ ,  $CL_z/F$ ,  $V_z/F$ , MRT,  $C_{ss, min}$ ,  $C_{ss, max}$ ,  $C_{ss, av}$ ,  $AUC_{ss}$ , DF and Rac of BB102 (and its main metabolites, if applicable); whether food has an effect on the exposure parameters (AUC0-inf, AUC0-t and  $C_{max}$ ) and the extent of effect.
- Efficacy of BB102 tablets (fasted or fed): ORR, DCR, duration of response (DOR), PFS, and OS.
- Relationship between biomarker and efficacy. Biomarkers include but are not limited to protein expression level, amplification, mRNA level and activating mutation profiles of FGF19 or FGFR4 in tumor tissues; bile acid precursors (e.g., 7-α-hydroxy-4-cholestene-3-one), total bile acids, total cholesterol, TG and serum FGF19 protein level in blood.
- Correlation between plasma concentration of study drug and OTcF (C-OTcF analysis).
- Metabolites of BB102.

#### 7.2 Expansion Trial

#### **Primary endpoints:**

• Efficacy of BB102 tablets (fasted): ORR, DCR, DOR, PFS and OS.

#### **Secondary endpoints:**

- **PK parameters of BB102 tablets (fasted):** T1/2, AUC0-t, AUC0-inf, Css, min, Css, max, Css, av, AUCss and DF of BB102 (and its main metabolites, if applicable).
- Safety of BB102 tablets (fasted): Incidences of all AEs and SAEs; abnormalities or changes in laboratory tests, vital signs, ECG, physical examination and ECOG score.
- Relationship between biomarker and efficacy. Biomarkers include but are not limited to protein expression level, amplification, mRNA level and activating mutation profiles of FGF19 or FGFR4 in tumor tissues; bile acid precursors (e.g., 7-α-hydroxy-4-cholestene-3-one), total bile acids, total cholesterol, TG and serum FGF19 protein level in blood.

# 8. Safety Evaluation

#### 8.1 AE

#### **8.1.1 Definition of AE**

AEs refer to any untoward adverse medical events following the use of the investigational product in subjects. It is manifested as symptoms, signs, diseases or abnormal laboratory findings, but it does not necessarily have a causal relationship with the investigational product.

#### Other considerations for AE:

### **Diagnoses versus signs and symptoms:**

• Each event should be recorded based on a single diagnosis. The accompanying signs (including abnormal laboratory values or ECG results) or symptoms should not be recorded as additional AEs. If the diagnosis is unknown, the signs or symptoms can be recorded as AEs accordingly.

